## **6. INVESTIGATIONAL PRODUCT**

Please refer to the most recent version the Investigator's Brochure (IB) for belumosudil for updated information. Given that ruxolitinib is a standard drug of choice for second line therapy, and is being administered as per SOC, please refer to the product monograph for additional, current information.

### **6.1 Drug Characteristics and Description**

Ruxolitinib is an orally available JAK-2 inhibitor which is a standard of care drug for second line therapy of cGVHD treatment.

Belumosudil inhibits ROCK2 and ROCK1 with 50% inhibitory concentration ( $IC_{50}$ ) values of approximately 100 nM and 3  $\mu$ M, respectively. ROCK2 has been shown to be activated in Th17-skewed milieu, leading to the upregulation of STAT3 phosphorylation and the consequent increased expression of Th17-specific transcription factors, such as ROR $\gamma$ t and IRF4. Moreover, selective ROCK2 inhibition restores immune homeostasis and shifts the Th17/Treg balance toward Tregs via a STAT5-dependent mechanism. Belumosudil also acts on the actin/myosin cytoskeletal network/impacts collagen

formation/mediates stress fiber formation and regulates the transcription of pro-fibrotic genes, including CTGF and  $\alpha$ -SMA. In vivo, belumosudil has demonstrated efficacy in a variety of clinically relevant animal models of disease including chronic GvHD, systemic sclerosis, idiopathic pulmonary fibrosis and other autoimmune diseases.

The first marketing authorization for belumosudil was obtained in the US in July 2021. The US FDA approved belumosudil (REZUROCK®) for the treatment of patients 12 years and older with cGVHD after failure of at least 2 prior lines of systemic therapy. Belumosudil was also approved for the same indication in Canada in March 2022.

## **6.2 Formulation**

Belumosudil, the investigational drug product, will be provided as a pale-yellow film-coated, oblong tablet containing 242.5 mg belumosudil mesylate salt (equivalent to 200 mg belumosudil free base), for oral administration.

## **6.3 Storage & Handling**

Belumosudil tablets are to be stored at a controlled room temperature of 20°C to 25°C (68°F-77°F) with excursions permitted between 15°C and 30°C (59°F-86°F). Supplies should be protected from moisture, freezing, strong light, and excessive heat within the provided containers. Supplies will be shipped under ambient conditions and should be stored in the site pharmacy. Based on current long-term and accelerated stability data, a shelf-life of 36 months is assigned for the belumosudil tablets when stored under 25°C/60% relative humidity (RH).

Ruxolitinib will be supplied, stored, and handled as per standard of care.

All medication must be stored in a secure area under the proper storage requirements with access restricted to the site staff pharmacist or designee(s).

## **6.4 Packaging and Labelling**

For this protocol, 200 mg belumosudil tablets will be supplied to participating sites in a white, wide-mouth high density polyethylene container with child-resistant, induction-seal screw cap lid containing integral desiccant.

The study drug will be labeled consistent with the regulatory requirements and local site guidelines.

## **6.5 Product Accountability and Destruction**

The PI (or an authorized designee) at each participating site must maintain a careful record of the inventory of the investigational product received using a drug accountability form. Investigational product accountability records will be available for review by the

study monitor as applicable according to the monitoring plan. The local site pharmacies will follow the appropriate GCP for the storage and dispensing of the medication to the study patient.

The investigational product should not be used for any purpose outside the scope of this protocol, nor can investigational product be transferred or licensed to any party not participating in the clinical study. Sponsor's data for investigational product are confidential and proprietary and shall be maintained as such by the QIs. The investigational product may be destroyed as per site's destruction policies and documentation of investigational product destruction will be filed in the trial master file. The investigational product may be returned to the Sponsor if requested by the Sponsor.

In accordance with regulatory requirements, study sites must document the amount of investigational product received from and returned to the sponsor, the amounts of investigational product dispensed to study patients, and the amount returned by study patients. Product accountability records must be maintained throughout the course of the study.

## **6.6 Drug Supply and Ordering**

The investigation product, Belumosudil, and funding for the study are being provided by Sanofi Canada. As ruxolitinib will be administered per standard of care, it should be obtained through to the site's local pharmacy. Sites must request study drug by submitting an order form to the drug depot, copying Ozmosis, in order for the study drug to be shipped to the site pharmacy. The PI (or designee) will verify and acknowledge receipt of all investigational product shipments by signing and returning all required forms.

## **7. MEASUREMENT OF DRUG EFFECTS**

### **7.1 Safety Assessment**

The adverse effects of the study drugs will be assessed from adverse events, vital signs and by clinically significant changes in the laboratory evaluations and ECGs.

Adverse events (AE) will use the descriptions and grading scales found in the revised NCI CTCAE. This study will utilize the CTCAE Version 5.0 for adverse event reporting.

### **7.2 Post-Baseline cGvHD Response Assessment**

The response assessment will be performed by the treating investigator according to the detailed schedule found in the study calendar. At each post-baseline visit, the response evaluation of each organ should be made by comparing the actual organ assessment versus the baseline status documented at C1D1. All organs that should be evaluated and

a high level summary of evaluation criteria as per NIH consensus guideline are listed in Table 6. Table 7 summarizes the rules for overall response assessment based on organ specific evaluation at each post-baseline visit.

**Table 6.** Organs included in cGVHD response assessment

Organ	Evaluation by	Criteria for response assessment
Skin	NIH Skin Score, considering %BSA involvement and sclerotic features	Change of skin score
Eyes	NIH Eye Score	Change of Eye score
Mouth	NIH Modified OMRS (Sum of scores for erythema, lichenoid and ulcers)	Change of OMRS
Esophagus	NIH Esophagus Score	Change of Esophagus score
Upper GI	NIH Upper GI Score	Change of Upper GI score
Lower GI	NIH Lower GI Score	Change of Lower GI score
Liver	Lab results for ALT, alkaline phosphatase, and Total bilirubin	Change of values for ALT, alkaline phosphatase, and Total bilirubin
Lungs	NIH Lung score AND %FEV1	Change of %FEV1
Joints and fascia	NIH Joint and Fascia Score and PROM scores	Change of Joint and Fascia Score and PROM scores

**Table 7.** Response determination for cGvHD based on all organs\*

Organ	Complete Response	Partial Response	Progression
Skin	NIH Skin Score 0 after previous involvement	Decrease in NIH Skin Score by 1 or more points	Increase in NIH Skin Score by 1 or more points, except 0 to 1
Eyes	NIH Eye Score 0 after previous involvement	Decrease in NIH Eye Score by 1 or more points	Increase in NIH Eye Score by 1 or more points, except 0 to 1
Mouth	NIH Modified Oral Mucosa Rating Score 0 after previous involvement	Decrease in NIH Modified Oral Mucosa Rating Score of 2 or more points	Increase in NIH Modified Oral Mucosa Rating Score of 2 or more points
Esophagus	NIH Esophagus Score 0 after previous involvement	Decrease in NIH Esophagus Score by 1 or more points	Increase in NIH Esophagus Score by 1 or more points, except 0 to 1
Upper GI	NIH Upper GI Score 0 after previous involvement	Decrease in NIH Upper GI Score by 1 or more points	Increase in NIH Upper GI Score by 1 or more points, except 0 to 1
Lower GI	NIH Lower GI Score 0 after previous involvement	Decrease in NIH Lower GI Score by 1 or more points	Increase in NIH Lower GI Score by 1 or more points, except from 0 to 1
Liver	Normal ALT, alkaline phosphatase, and Total bilirubin after previous elevation of one or more	Decrease by 50%	Increase by 2x ULN
Lungs	-Normal %FEV1 after previous involvement -If pulmonary function tests (PFTs) not available, NIH Lung Symptom Score 0 after previous involvement	-Increase by 10% predicted absolute value of %FEV1 -If PFTs not available, decrease in NIH Lung Symptom Score by 1 or more points	- Decrease by 10% predicted absolute value of %FEV1 -If PFTs not available, increase in NIH Lung Symptom Score by 1 or more points, except 0 to 1
Joints and Fascia	Both NIH Joint and Fascia Score 0 and P-ROM score 25 after previous involvement by at least one measure	Decrease in NIH Joint and Fascia Score by 1 or more points or increase in P-ROM score by 1 point for any site	Increase in NIH Joint and Fascia Score by 1 or more points or decrease in P-ROM score by 1 point for any site
Global	Clinician overall severity score 0	Clinician overall severity score decreases by 2 or more points on a 0–10 scale	Clinician overall severity score increases by 2 or more points on a 0–10 scale

\* At least one organ must be involved at baseline. Organ specific responses versus baseline status

Abstracted from: Lee SJ, Wolff D, Kitko C, et al. *Biol Blood Marrow Transplant* 2015; 21:984 –999.

### **7.3 Response Duration**

Response duration will be defined as the time from the first documented achievement of complete response (CR) or partial response (PR), whichever occurs first (as defined in Table 7), until the first documented date of loss of response or disease progression. The smallest measurements recorded during the study, including baseline, will serve as the reference for assessing progression.

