**Figure 1. Participant treatment schema**

## 3. OBJECTIVES

Primary Objectives	Primary Endpoints
To evaluate efficacy, tolerability and safety of combination treatment of belumosudil with ruxolitinib as second line therapy for steroid-refractory cGvHD.	
 
Efficacy will be assessed using overall response rate (ORR) as per the NIH cGvHD Consensus Response Criteria at 24 weeks of combination treatment (C8D1) of belumosudil with ruxolitinib (i.e., 28 weeks after C1D1).
 
Tolerability and safety will be assessed by the incidence and severity of adverse events (AEs) throughout the treatment duration using CTCAE v5.0 grading.
 

Secondary Objectives	Secondary Endpoints
To evaluate the response achievement with combination treatment of belumosudil with ruxolitinib as second line treatment for cGvHD.	
 
ORR as per the NIH cGvHD Consensus Response Criteria after 48 weeks of combination treatment of belumosudil with ruxolitinib (i.e., 52 weeks after C1D1).
 
Failure-free survival (FFS) after 24 and 48 weeks of combination treatment of belumosudil with ruxolitinib (i.e., 28 and 52 weeks after C1D1). FFS is defined as the time from treatment initiation until the occurrence of treatment failure.
 
Durable response rate in patients who achieve complete or partial response with combination treatment of belumosudil with ruxolitinib as assessed at 52 weeks from
 

	
C1D1. Durable response is defined as sustained improvement in symptoms or absence of disease progression from the time of treatment initiation.
 
4. Overall GvHD symptom burden improvement, serially measured with a modified Lee Symptom Scale (see Appendix D).

Exploratory Objectives	Exploratory Endpoints
To evaluate improvement in musculoskeletal involvement of sclerotic GvHD using the P-ROM score measurement.	1. Changes in the P-ROM score after 12, 24, and 48 weeks of combination therapy in patients who have developed sclerotic GvHD in musculoskeletal involvement of GvHD

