## 11.3 Evaluation of Study Endpoints

### 11.3.1 Evaluation of the Primary and Secondary Endpoints

Overall response rate (ORR) will be evaluated at 24 and 48 weeks after combination therapy (i.e. 28 and 52 weeks after enrollment), respectively. The proportion of responders and its 95% confidence interval (using exact binomial methods) will be calculated.

Failure-free survival (FFS) will be evaluated using Kaplan-Meier method. The FFS rate will be evaluated at 24 and 48 weeks after combination therapy (i.e. 28 and 52 weeks after enrollment), The composite endpoint of failure is defined as 1) GvHD progression or loss of response requiring switch of systemic GvHD treatment, 2) relapse of primary hematologic disease and 3) non-relapse mortality.

Durable response after response achievement will be evaluated only in the patients achieved CR or PR (any response). The Kaplan-Meier estimate will be calculated from the date of CR/PR achievement to the date of losing response/progression or death from any cause.

GvHD symptom burden improvement, measured serially by the modified Lee Symptom Scale, will be evaluated using repeated measure based on the general linear model. If p-value is less than 0.05, it demonstrates statistically significant change over time within subject.

The Modified Lee symptom score (mLSS) will be used to reflect a symptom burden in cGvHD study patients. The symptoms will be assessed serially and will be evaluated using repeated measure based on the general linear model. If p-value is less than 0.05, it demonstrates statistically significant change over time within subject. The score assesses 7 different organs/areas including skin, eye/mouth, breathing, eating/digestion, muscle/joints, energy, and mental/emotional health. The sum of these domains will be calculated to derive the total mLSS. Clinically meaningful improvement in mLSS is defined as a reduction of  $\geq 7$  points in overall mLSS. Longitudinal change in mLSS is analyzed by repeated measures using generalized linear model over time, evaluating within-subject and between-subject effects. In addition, the proportion of the patients showing clinically meaningful improvement in mLSS is analyzed longitudinally at 12, 24, and 48 weeks. In addition, the best improvement in mLSS is also calculated in each subject and plotted.

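### Section 7.3 measures progression from the smallest value on study, which is the worst value for %FEV1 and P-ROM and conflicts with the C1D1 reference in Section 7.2

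*Protocol*

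**What the plan says.** Section 7.3 of the protocol runs response duration from the first CR or PR to loss of response or progression, and then fixes the reference: "The smallest measurements recorded during the study, including baseline, will serve as the reference for assessing progression". No organ or measure is exempted.

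Section 7.2 fixes a different reference. Each organ is evaluated at every post-baseline visit by "comparing the actual organ assessment versus the baseline status documented at C1D1". The footnote to Table 7, the table that holds the Progression column, says the same: "Organ specific responses versus baseline status".

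Table 7 also fixes the direction of each measure. Lung progression is "Decrease by 10% predicted absolute value of %FEV1" and lung partial response is "Increase by 10% predicted absolute value of %FEV1". Joint and fascia progression is "Increase in NIH Joint and Fascia Score by 1 or more points or decrease in P-ROM score by 1 point for any site", and a P-ROM score of 25 is part of complete response. High is therefore good for %FEV1 and P-ROM. For the skin, eye, mouth and GI scores, the liver tests, the NIH joint score and the lung symptom score, high is bad.

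Durable response is a secondary endpoint. Section 3, repeating the Synopsis, says: "Durable response is defined as sustained improvement in symptoms or absence of disease progression from the time of treatment initiation". Section 11.3.1 says: "The Kaplan-Meier estimate will be calculated from the date of CR/PR achievement to the date of losing response/progression or death from any cause".

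**The concern.** A smallest-value reference makes sense where a small value is the good one. For %FEV1 and P-ROM it is the bad one, so the reference moves down with the patient, and a slow decline is always compared with a value that has already declined. For the other measures the rule works in the intended direction, but it compares with the best value on study, whereas Section 7.2 compares with C1D1. One visit can then be a response under one section and progression under the other.

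The progression date ends response duration and is an event in the durable-response Kaplan-Meier analysis. Lung and joint disease matter here because Section 1.2 expects belumosudil to add benefit in organs affected by fibrosis. If the choice between the two references is left until the data are in, durability depends on a decision made with results in view.

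**Working it through.** The protocol gives no figure to reproduce. The check applies the Table 7 thresholds to short illustrative series (not trial data) under both references.

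**Rules**
- Reference A (Section 7.2, Table 7 footnote): change = current value − C1D1 value.
- Reference B (Section 7.3): change = current value − smallest earlier value, C1D1 included. If the current value also counted, a fall below the reference would be impossible, so this is the reading more favourable to the protocol.
- Progression: %FEV1 change of −10 or lower; P-ROM change of −1 or lower at a site; skin score change of +1 or higher, except 0 to 1.

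**Lung, steady decline (50 at C1D1)**

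| Value | A | B |
|---|---|---|
| 46 | −4 | 46 − 50 = −4 |
| 40 | −10, progression | 40 − 46 = −6 |
| 36 | −14, progression | 36 − 40 = −4 |

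Under B the threshold is never met, despite a loss of 14 points. Such a patient enters response duration only through improvement in another organ, so a lung responder is the cleaner test.

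**Lung, responder who then declines (50 at C1D1)**

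| Value | A | B |
|---|---|---|
| 65 | +15, response | +15 |
| 44 | −6 | 44 − 50 = −6 |
| 40 | −10, progression | 40 − 44 = −4 |
| 36 | −14, progression | 36 − 40 = −4 |

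The patient loses 65 − 36 = 29 points from the best value, with no lung progression under B. Five values fit the Study Calendar, which schedules pulmonary function tests at C1D1 and weeks 16, 28, 40 and 52.

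**P-ROM, one site (4 at C1D1)**

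| Value | A | B |
|---|---|---|
| 3 | −1 | −1 |
| 6 | +2, response | 6 − 3 = +3 |
| 3 | −1, progression after response | 3 − 3 = 0 |

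The fall after the response is missed because the earlier low has become the reference. Without an earlier low there is no miss against C1D1: until a value first drops below C1D1, the smallest earlier value is the C1D1 value itself, and the threshold is one point. An enumeration agrees. It took all series of a baseline plus four visits at one site, with a range of 1 to 7 that the protocol does not state. Of 12,131 series that progress against C1D1, counted from C1D1, rule B misses or delays none. Of 5,411 that progress against C1D1 after a response, B records no post-response progression in 1,120. These are unweighted counts of possible series, not patient frequencies.

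**Skin, where high is bad (3 at C1D1)**

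| Value | A | B |
|---|---|---|
| 1 | −2, partial response | −2 |
| 2 | −1, still partial response | 2 − 1 = +1, progression |

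**Durable response, side by side**

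| Place | Starts | Ends or fails at |
|---|---|---|
| Synopsis, Section 3 | Treatment initiation | Improvement not sustained, or progression (joined by *or*) |
| Section 7.3 | First CR or PR | Loss of response or progression; death not named |
| Section 11.3.1 | CR or PR | Loss of response, progression or death |

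**The case against.** The strongest reply is that other text catches many of these patients. Section 7.2 still compares every visit with C1D1, so the fall to 40 is recorded as lung progression at that visit. Section 7.3 also ends duration at loss of response, a separate trigger. Section 5.6 counts a lack of response or a mixed response as a progression event in the analysis, and a patient improving elsewhere while the lung worsens would naturally be called mixed. All of this stands and limits the effect. It does not settle the matter: Section 7.3 gives loss of response no rule, and Section 5.6 does not say which reference applies.

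The joint part is also limited. A first fall in P-ROM below C1D1 is always caught, and a rise in the NIH joint score can flag worsening independently, with the smallest value being the right direction for that score. When pulmonary function tests are unavailable, the lung symptom score does the same for the lung.

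A reader might infer more than the protocol supports on three points:
- That a P-ROM gain followed by a return to the starting value, such as 5, 7, 5, is progression lost through Section 7.3. It is not progression against C1D1 either.
- That, under Section 3, a patient who has lost a partial response without falling below baseline still counts as durable. Section 5.6 undercuts this, since lack of response is a progression event for analysis.
- That the protocol errs by not saying how new systemic therapy enters the durability analysis. That detail is commonly left to the statistical analysis plan, which is not at hand.

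**Conclusion.** The Section 7.3 reference is wrong as written. It points the wrong way for %FEV1 and P-ROM, and it contradicts Section 7.2 and the Table 7 footnote for every measure.

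The clearest consequence is in the lung: a decline in steps of under 10 points per test never meets the Section 7.3 progression rule, however large the total loss. For P-ROM the consequence is confined to a fall after an earlier low. For measures where high is bad, the conflict runs the other way and progression is declared sooner than against C1D1.

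The reach is response duration and the durable-response Kaplan-Meier analysis. Week-24 ORR follows Section 7.2 and is not affected. It might be inferred that durability is overstated overall; that cannot be shown, because the direction differs by organ and the protocol gives no data on how often such series occur. The conclusion rests on reading Section 7.3 literally and on treating a fall of exactly 10 points in %FEV1 as meeting the threshold.

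**What to change.** 1. In Section 7.3, delete the smallest-value sentence and judge progression by Table 7 against C1D1. If a best-on-study reference is intended instead, replace smallest by best and state the direction per measure: lowest for symptom scores and liver tests, highest for %FEV1 and P-ROM.
2. Reconcile Sections 5.6, 7.2 and 7.3 on that one reference, and say that it also governs loss of response, lack of response and mixed response.
3. Align the durable-response wording in the Synopsis, Section 3 and Section 7.3 with Section 11.3.1: from first CR or PR to loss of response, progression or death. Drop the alternative that accepts absence of progression since treatment initiation.

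The cost is protocol wording; no new data are needed. The downside is that reported durability may be shorter.

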### **7.4 Optional Sub-Study Correlative Sample Collection**

All patients who agree to participate in this study, will be presented with the option to participate in an optional sub-study that will involve the collection of additional blood samples. The correlative blood samples will be obtained as per the frequency in the Study Calendar. These samples will be sent to a tissue biobank in Toronto, Canada and stored here for up to 10 years for future research purposes. Access to samples in long term storage (for patients who consented) will be restricted to representatives delegated by the PI. Samples will be de-identified by using a unique patient number. Further details will be provided in the study laboratory manual, including sample shipment details.

